## Project Summary

### Description of the Project

#### 1.1 Rationale and objectives of the study

##### 1.1.1 Rationale

Paracervical block (PCB) is a widely used, but largely unstandardized technique for pain management in gynecological procedures. From hysteroscopy to first trimester abortion procedures to dilator placement for dilation and evacuation, providers utilize the paracervical block to manage cervical dilation pain. However for such a widely used technique, the exact method is often provider or site specific. A 2009 survey of National Abortion Federation members i illustrates that the volume alone of anesthetic used for PCB in first trimester abortion procedures varies tremendously amongst providers. That said, research published over the last few years has had enormous impact on global guidelines, such as those published by Ipas. New techniques for paracervical block that focus on limiting symptoms and resources while also ensuring adequate pain management are needed to improve care for women around the world.

A randomized controlled trial done by Renner et al. in 2012ii demonstrated that a 4-site, 18 mL 1% lidocaine paracervical block, with a 2 mL injection for tenaculum placement, used during first-trimester surgical abortions was beneficial in reducing pain due to cervical dilation when compared to sham paracervical block. The block technique endorsed by Renner et al. was based on findings from a combination of studies about paracervical block that investigated variations in needle injection siteiii, type of lidocaineiv, depth of lidocaine injectionv, general vs. local anesthesiavi, and wait time between injection and procedurevii. Missing from consideration, however, was the *volume* of lidocaine necessary to achieve a reduction in dilation pain. The final technique used in Renner et al.'s study was as follows:

- Syringe loaded with 18 mL of 1% plain lidocaine buffered with 2 mL 8.4% sodium bicarbonate (20 mL total); 20-gauge spinal needle
- 2 mL injected at the tenaculum site, 12 o'clock superficially into the cervix
- The tenaculum is immediately placed at 12 o'clock
- The remaining 18 mL are injected slowly over 60 seconds into the cervicovaginal junction in four equal aliquots at 2, 4, 8, and 10 o'clock; the injection is continuous from superficial to deep (3 cm) to superficial (injecting with insertion and withdrawal)
- Dilation begins 3 minutes after application of the block

A subsequent study done by Renner et al. in 2016viii aimed to further refine this technique and looked at both the 3-minute wait time and the use of 4-site versus 2-site injection. Results of the study were largely inconclusive, suggesting that no wait time is no worse than a three-minute wait and that 2-site and 4-site injections may be interchangeable. Despite these findings, global guidelines and provider preference continue to follow findings from Renner et al.'s 2012 study.

As the dangers of lidocaine injection are minimal, but not absent, and the administration of a paracervical block is painful and time-consuming, we propose comparing a technique similar to

the one put forth by Renner et al. with one that has been used in multiple Stanford studies and notably employs a smaller volume of lidocaine and only two injection sites. The technique is as follows:

- Syringe loaded with 12 mL of 1% lidocaine (120 mg); 22-gauge spinal needle
- 2 mL injected at the tenaculum site, either 6 or 12 o'clock superficially into the cervix
- The tenaculum is immediately placed at the previously injected site
- The remaining 10 mL are slowly injected into the cervicovaginal junction in two equal aliquots at 4 and 8 o'clock; the injection is continuous from superficial to deep (3 cm) to superficial (injecting with insertion and withdrawal)
- No wait time between injection and dilator insertion

We aim to compare this technique with one similar to Renner et al.'s technique from 2016:

- Syringe loaded with 20 mL of 1% lidocaine (120 mg); 22-gauge spinal needle
- 2 mL injected at the tenaculum site, either 6 or 12 o'clock superficially into the cervix
- The tenaculum is immediately placed at the previously injected site
- The remaining 18 mL are slowly injected into the cervicovaginal junction in two equal aliquots at 4 and 8 o'clock; the injection is continuous from superficial to deep (3 cm) to superficial (injecting with insertion and withdrawal)
- No wait time between injection and dilator insertion

Our justification for this proposed technique comparison is as follows:

With regards to smaller dosage, there is much research to be done. While the lidocaine label recommends a maximum dose of 200 mg (20 mL at 1%) of lidocaine per 90-minute period for paracervical block,ix it does not recommend a minimum dose. Renner et al.'s 2012 studyii provides evidence for paracervical block over sham for cervical dilation pain and Chanrachakul's 2001 studyx provides evidence that pain relief comes from both lidocaine and distention rather than distention alone. These studies point to the benefit of using lidocaine, but to date there is little data providing the optimal dose between 0 mL and 20 mL. With this knowledge, we propose the use of 10 mL of lidocaine in order to maintain the use of lidocaine for pain control, but minimize symptoms (such as metallic taste, ringing in the ears, and at worst, seizure or cardiac arrest) that are more likely to manifest with 20 mL.

With regards to 2-site versus 4-site, our aim is to build on the findings from Glantz and Shomento's 2001 study and Renner et al.'s 2016 study. Glantz and Shomento's study from 2001iii contained four study arms and looked at both 1% chloroprocaine versus placebo and 4-site versus 2-site injection. While the original paper concluded that PCB with chloroprocaine provides more pain relief than saline for both 4-site and 2-site injections, subsequent reanalysis from 2009xi showcased that preference for 4-site or 2-site versus saline depended on the time point at which pain was measured. Regardless, more importantly, the findings showed that when comparing 4-site 1% chloroprocaine block to 2-site 1% chloroprocaine block, there is no statistical difference. Furthermore, Renner et al.'s 2016 studyviii, which compared 20 mL of 1% buffered lidocaine at 4-site versus 2-site, showcased that using noninferiority analysis, there is no statistical difference between 4-site and 2-site block. Additionally, while superiority analysis demonstrated that 4-site is statistically superior to 2-site for pain control at cervical dilation, this

demonstrated difference is not clinically significant. All in all, these data point toward the clinical conclusion that 2-site may be utilized in place of 4-site. Our proposed technique follow findings from these studies and if proven effective, would result in fewer painful injections during paracervical block.

Concerning depth of injection, we will utilize the 3 cm depth as used in Renner's studies. Wiebe et al.'s 1992 studyiv and Cetin and Cetin's 1997 studyv suggest utilizing deep injection, as dilation pain scores were lower for deep injection in both studies.

Phair et al.'s 2002 studyxii and Renner et al.'s 2016 studyviii both showcased that there is no significant difference in pain with cervical dilation when comparing no-wait between PCB injection and cervical dilation to wait. As such, we have opted to exclude a wait time.

With regard to plain lidocaine versus buffered lidocaine, while several studies have showcased the benefit of utilizing buffered lidocaine instead of plain lidocaineiv, given the high cost and prolonged preparation time associated with creation of a buffered lidocaine solution, we have decided to use 1% plain lidocaine. Our hope is that by showcasing pain control with a more cost-effective anesthetic, our results will be generalizable to a larger global audience.

Finally, while many studies focus on pain control in first-trimester abortion, including Renner et al., in order to isolate cervical dilation pain from uterine pain, we have chosen to focus on the cervical preparation procedure needed prior to a second trimester surgical abortion rather than the surgical procedure itself. Need for additional research in this timeframe was highlighted in Soon et al.'sxiii work, which demonstrated that the paracervical block technique utilized by Renner et al. was effective in reducing pain associated with osmotic dilator insertion prior to second trimester abortion. We also believe that isolating the pain of the cervical dilation procedure will allow us to generalize the findings of our study to be meaningful for any procedure in which cervical dilation is necessary.

### **1.1.2 Objectives and hypothesis**

We hypothesize that a 2-site, 12 mL 1% plain lidocaine injection paracervical block (PCB) technique (2 mL for tenaculum placement, 10 mL for paracervical block) will provide non-inferior pain control compared to a previously established 2-site, 20 mL 1% lidocaine injection PCB (2 mL for tenaculum placement, 18 mL for paracervical block) when administered for dilation pain control during cervical preparation.

Our primary objective is to determine pain perceived at time of dilator insertion measured by Visual Analogue Scale (VAS; Dilator Insertion: Immediately following dilator insertion) (0-100mm).

Secondary objectives include assessing:

- Pain perceived at additional time points before, during, and after the procedure (all measured by VAS (0-100mm; 0 being no pain and 100 being worst pain imaginable):
  - o Anticipated Pain: 30 minutes prior to procedure

- Baseline Pain: Immediately prior to procedure
- Block injection Pain: Immediately following injection, but prior to dilator insertion
- Post-procedure Pain: 10-15 minutes following procedure
- Overall Pain: Assessed after procedure (prior to discharge)
- Total procedure time, as defined by speculum time
- Incidence of complications
  - Inability to dilate cervix
  - Seizure
  - Cardiac arrest
  - Structural trauma (uterine perforation, cervical laceration, etc.)
  - Hemorrhage (EBL estimation)
- Symptom Data
  - Following block injection, any experience of:
    - Metallic taste in mouth
    - Ringing in ears
    - Lightheadedness
- Any other systemic symptoms experienced, including vasovagal reaction
- Provider reported ease of insertion
- Global satisfaction (acceptability) of procedure reported by participant (VAS, 0-100mm; 0 being unsatisfied and 100 being fully satisfied)

## 1.2 Design and methodology

### 1.2.1 Research design and General Methodological Approach

This is a non-inferiority, single blinded, randomized controlled trial.

### 1.2.2 Criteria for the selection of subjects

Women who need dilator placement for second trimester D&E procedures will be invited to participate in the study protocol. This population was chosen because our aim is to isolate how best to manage cervical dilation pain and not uterine aspiration pain, which is potentially a confounding factor when analyzing pain perceived during first trimester abortions rather than cervical dilation procedures alone. Additionally, we will limit our study population to those women presenting for an abortion  $\geq 16$  weeks gestation. This population was selected as they typically require more dilators than the patients at lower gestational ages.

Specific inclusion criteria:

- Women 18 and older
- Intrauterine pregnancy  $\geq 16$  weeks gestation
- English speaking competency
- Willing and able to sign consent forms
- Agree to comply with study procedures

### 1.2.3 Subject recruitment and allocation

Subjects will be recruited from Stanford Gynecology Clinic in Palo Alto, California and at Planned Parenthood Mar Monte in San Jose, CA.

- At Stanford, potential participants will be identified by prospective chart review done by clinical research coordinators. Once identified, clinical research coordinators will obtain permission from provider to speak with participants.
- At Planned Parenthood, clinic staff will notify clinical research coordinators of potential participants.

To ensure even allocation across sites, two randomization schemes will be created, one for each site.

#### **1.2.4 Description of the drugs and devices to be studied**

Xylocaine (lidocaine HCl) is a common local anesthetic that works by stabilizing the neuronal membrane by inhibiting the ionic fluxes required for the initiation and conduction of impulses. Local anesthetics of the amide type are thought to act within the sodium channels of the nerve membrane. According to the packaging insert, anesthesia is achieved within 5 minutes, depending on the area of application, and duration of anesthesia is approximately 20-30 minutes.

For paracervical block the drug label recommends a maximum dose of 200 mg (100 mg per side) in a 90 minute periodix. Given risk of rapid systemic absorption and possible maternal seizure and cardiovascular collapse, the maximum dose should not be exceeded. The label also recommends slow injection and a 5-minute interval between each side.

Contraindications to lidocaine include the following:

- Hypersensitivity to lidocaine or any component of the formulation
- Hypersensitivity to another local anesthetic of the amide type
- Adam-Stokes syndrome
- Wolff-Parkinson-White syndrome
- Severe degrees of SA, AV, or intraventricular heart block (except in patients with a functioning artificial pacemaker)
- Premixed injection may contain corn-derived dextrose and its use is contraindicated in patients with allergy to corn or corn-related products

#### **1.2.5 Admission procedure**

Eligible women will be screened and identified in two ways. The first will be via prospective chart review done by Stanford clinical research personnel. The second will be providers and clinic staff informing clinical research personnel of potential participants.

If potential participants meet inclusion criteria and permission has been granted by their provider, they will be approached by a clinical research coordinator who will review the study protocol and obtain informed consent. After obtaining informed consent, participants will be randomized to a study arm via computer-generated block randomization using REDCap

software. The provider and staff will be aware of arm allocation, but participants will remain blinded.

There will be two study arms:

Experimental:

- Syringe loaded with 12 mL of 1% lidocaine (120 mg); 22-gauge spinal needle
- 2 mL injected at the tenaculum site, either 6 or 12 o'clock superficially into the cervix
- The tenaculum is immediately placed at the previously injected site
- The remaining 10 mL are slowly injected into the cervicovaginal junction in two equal aliquots at 4 and 8 o'clock; the injection is continuous from superficial to deep (3 cm) to superficial (injecting with insertion and withdrawal)
- No wait time between injection and dilator insertion

Control:

- Syringe loaded with 20 mL of 1% lidocaine (120 mg); 22-gauge spinal needle
- 2 mL injected at the tenaculum site, either 6 or 12 o'clock superficially into the cervix
- The tenaculum is immediately placed at the previously injected site
- The remaining 18 mL are slowly injected into the cervicovaginal junction in two equal aliquots at 4 and 8 o'clock; the injection is continuous from superficial to deep (3 cm) to superficial (injecting with insertion and withdrawal)
- No wait time between injection and dilator insertion

Prior to the procedure, clinical research coordinators will obtain the following baseline information using REDCap:

- Demographics
  - Location of procedure
  - MRN
  - Date enrolled
  - First name
  - Last name
  - Date of birth
  - Age
  - Phone number
  - Race
  - Ethnicity
- Medical History (Physical Exam and Ob/Gyn History)
  - Height
  - Weight
  - BMI
  - First day of last menstrual period
  - Gestational age defined by U/S
  - Medication allergies
  - Current medications
  - Number of previous pregnancies
    - Number of previous vaginal deliveries

- Number of previous cesarean sections
- Number of previous abortions
- Number of previous abortions after 16 weeks gestation
- Number of miscarriages
- Recent deliveries
- Medical problems
- Previous surgeries
  - Previous cervical surgeries
  - Other previous surgeries

The participant will then be prepped for the procedure. At that point, the clinical research coordinator will accompany participants throughout the duration of their procedure and obtain the following information:

- Procedure Data
  - Provider type (i.e. resident, fellow, attending)
  - Provider reported ease of procedure
  - Initial cervical dilation
  - Uterine position
  - Number of osmotic dilators placed
  - Total procedure time, as defined by speculum time
  - Digoxin given
  - Complications
    - Inability to dilate cervix
    - Seizure
    - Cardiac arrest
    - Structural trauma (uterine perforation, cervical laceration, etc.)
    - Hemorrhage (EBL estimation)
  - Administration of Mifepristone for cervical preparation
- Procedure VAS Data
  - Anticipated Pain: 30 minutes prior to procedure
  - Baseline Pain: Immediately prior to procedure
  - Block injection Pain: Immediately following injection, but prior to dilator insertion
  - Dilator Insertion Pain: Immediately following dilator insertion
  - Post-procedure Pain: 10-15 minutes following procedure
  - Overall Pain: Assessed after procedure (prior to discharge)
- Symptom Data
  - Following block injection, any experience of:
    - Metallic taste in mouth
    - Ringing in ears
    - Lightheadedness
  - Any other systemic symptoms experienced, including vasovagal reaction
- Acceptability Data
  - Global satisfaction with procedure
- Recognition of group allocation

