## **1.2.11 Number of subjects and statistical power**

88 participants are required to be 80% sure that the lower limit of a one-sided 97.5% confidence interval (or equivalently a 95% two-sided confidence interval) will be less than the non-inferiority limit of 15mm. Accounting for participant drop-out, we will recruit 96 women to participate in this study (significance level, alpha of 5%; power of 80%; standard deviation of 28; non-inferiority limit of 15).

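### As narrated in section 1.2.5, randomisation (arm known to provider and staff) comes before the pre-procedure history and pain scores, which needlessly allows post-randomisation losses and early staff knowledge of the arm

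*Combined protocol and SAP*

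**What the plan says.** Section 1.2.5 (Admission procedure) describes screening, approach and consent, and continues: "After obtaining informed consent, participants will be randomized to a study arm", by computer-generated blocks in REDCap. The next sentence reads: "The provider and staff will be aware of arm allocation, but participants will remain blinded".

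After listing the two arms, the section turns to demographics and medical history: "Prior to the procedure, clinical research coordinators will obtain the following baseline information using REDCap". The woman is then prepared for the procedure, and the coordinator's role is given as: "At that point, the clinical research coordinator will accompany participants throughout the duration of their procedure and obtain the following information". The list that follows includes "Anticipated Pain: 30 minutes prior to procedure" and "Baseline Pain: Immediately prior to procedure", then the pain scores at and after the block.

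Other sections that bear on the point:

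- Section 1.1.2 lists anticipated and baseline pain as secondary measures. The primary measure is pain at dilator insertion.
- Section 1.2.7 discontinues women for certain events during the dilation procedure. It does not mention women lost before it.
- Section 1.2.10 compares VAS scores by t-tests and non-parametric tests, and adds a regression to find what predicts pain. It names no covariates and defines no analysis population.
- Section 1.2.11 states: "Accounting for participant drop-out, we will recruit 96 women to participate in this study". The evaluable number is 88.
- Section 1.2.12 acknowledges that providers cannot be blinded because the volumes differ.

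**The concern.** Providers cannot be blinded to the volume they inject, but that limit starts when the syringe is loaded. The narrative makes the arm known earlier, and two things follow.

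1. **Losses.** A woman who changes her mind, or whose procedure is cancelled, between randomisation and the block has already been allocated. She has no dilator-insertion score, and the plan does not say whether or how she is counted. If staff know the arm, such losses need not be alike in the two arms. Had she left before randomisation, she could not affect the comparison.
2. **Contact before the scores.** Staff who know the arm can deal with the woman before she gives her anticipated and baseline scores. Section 1.5 expects some reluctance about being allocated the smaller dose, so differing reassurance is conceivable. A score meant to describe the woman before treatment should be beyond the reach of allocation.

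In a non-inferiority trial, it is worth closing off avoidable routes by which the arms could drift apart or together.

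**Working it through.** **Step 1. The order, side by side (section 1.2.5).**

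| Step as narrated | Timing given | Position relative to randomisation |
|---|---|---|
| Consent | None | Before (explicit) |
| Randomisation; provider and staff know the arm | After consent; no interval | – |
| Demographics and history | Before the procedure | Described after; not stated |
| Preparation; coordinator accompanies the woman | After history | Described after; not stated |
| Anticipated-pain VAS | 30 minutes before the procedure | Described after; not stated |
| Baseline VAS | Immediately before the procedure | Described after; not stated |
| Block | – | After |

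The only explicit link is that randomisation follows consent. The rest comes from the order of the text, but no sentence points the other way and none withholds the arm until the scores are saved. If the narrative order is followed, at least 30 minutes separate randomisation from the procedure.

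**Step 2. Is the arm needed earlier?** The arms differ in the volume loaded and injected. Consent, history, preparation and the two pre-procedure scores are the same in both. Nothing described before syringe loading uses the allocation.

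**Step 3. Are losses in that interval covered?** The discontinuation rule in section 1.2.7 concerns the dilation procedure. Section 1.2.10 defines no analysis set. A woman randomised but not treated therefore falls under no rule.

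**Step 4. The plan's own numbers.** Inputs from section 1.2.11 are SD 28 mm, margin 15 mm and power 80%. A true difference of 0 and 1:1 allocation are assumed.

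- n per arm = 2 × (z for alpha + z for power)² × (SD / margin)².
- One-sided 5%: 2 × (1.645 + 0.842)² × (28/15)² = 43.1, so 44 per arm and 88 in total. This reproduces the plan.
- One-sided 2.5%, the interval that the text describes: 2 × (1.960 + 0.842)² × (28/15)² = 54.7, so 55 per arm and 110 in total. That mismatch is a separate matter, and this point does not depend on it.
- Drop-out allowance: 96 − 88 = 8, and 8/96 = 8.3%.

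The documents do not say how many of the 8 are expected before the block. The share could be anything from 0 to 8.

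**Step 5. Illustration of the loss route (assumed inputs, not an estimate).** Suppose k of 48 women in one arm are lost, and their pain would have differed by D from that of the women who remain. The mean of those who remain then differs from the mean of all allocated to that arm by (k/48) × D.

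- k = 4: D = 14 mm (0.5 SD) gives 1.2 mm; D = 28 mm (1 SD) gives 2.3 mm.
- k = 8: D = 14 mm gives 2.3 mm; D = 28 mm gives 4.7 mm.

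The lower end is 0, if no one is lost before the block or those lost resemble the rest. The upper end puts the whole allowance in one arm, before the block, with a full SD of difference. That is an extreme case, and it is still below the 15 mm margin.

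**The case against.** The case on the other side is substantial, and most of it stands.

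- **The order is inferred.** The text gives no interval after consent, and it times the scores against the procedure, not against randomisation. This stands. If the team already intends to randomise late, the text does not say so.
- **The scores come from blinded women.** They are self-reported, and participants' recognition of their allocation is recorded as a check. Knowledge of the arm could act only through staff behaviour, or through a coordinator whose knowledge of the arm is not stated. This stands. Most history items are factual and hard to influence. The provider will know the arm during injection and dilation in any case, so later randomisation removes only the earlier part of the exposure.
- **There is no planned path to the primary result.** A reader might infer that contaminated baseline scores would bias the primary comparison through covariate adjustment. The plan specifies an unadjusted comparison, and its regression names no covariates, so the documents do not support that reading.
- **Drop-out has other named sources.** Section 1.2.7 removes women for events during dilation, and section 1.5 expects difficulty in obtaining scores. Later randomisation prevents neither. Inclusion criteria are also to be met before the approach, which narrows the route of late ineligibility.
- **No power gain follows.** A reader might infer that avoiding all 8 losses lifts the evaluable number from 88 to 96. By noncentral t, power would then go from 80.2% to 83.2% at one-sided 5%, or from 70.0% to 73.8% at one-sided 2.5%. But a woman who leaves before the block has no primary score whenever she would have been randomised. If 96 counts women at consent, the evaluable number does not change. If it counts women randomised, any gain requires consenting more women, and its size depends on the unknown share lost before the block.

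What is left unanswered is that the arm is not needed until the syringe is loaded, and that women randomised but lost before the block have no rule.

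**Conclusion.** The point holds as a modest design improvement. As narrated, allocation and staff knowledge of it come earlier than anything in the procedure requires. That allows avoidable post-randomisation losses with no analysis rule, and contact with informed staff before two pre-procedure scores are given.

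The losses are the more material part. Their number before the block is unknown (0 to 8 of the allowance), and the shift of 0 to 4.7 mm in one arm's mean rests wholly on assumed inputs. Any effect on the two scores is indirect and cannot be sized from the documents.

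The documents do not support saying that the baseline scores are biased, that the primary estimate is compromised, or that power would rise. The conclusion rests on reading the order of section 1.2.5 as the order of events.

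**What to change.** In section 1.2.5, move the randomisation sentence. REDCap randomisation is performed, and the arm released, only after eligibility, history, the anticipated-pain VAS and the baseline VAS are saved, and immediately before the syringe is loaded.

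Three short statements would complete the change:

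- whether the coordinator who collects the scores knows the arm;
- how a woman randomised but not treated is analysed, since a few may remain;
- whether the 96 in section 1.2.11 counts women consented or women randomised.

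The cost is a one-paragraph amendment, a reordering of the REDCap forms and a short wait while the syringe is loaded after the baseline score. The treatment in either arm is unchanged. If 96 is taken to mean women randomised, some additional women may have to be consented to reach it.

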## **1.2.7 Criteria for discontinuation**

Participants requiring additional cervical anesthesia or intervention due to complication during the dilation procedure will be discontinued from the study.

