### **1.6 Expected outcomes of the study and dissemination of findings**

If our hypothesis is true, our technique will be seen as non-inferior to a technique of cervical block using 20 mL 2-site injection to control cervical dilation pain. The implications of these findings give evidence for a new technique and could have large implications in terms of cost-savings, pain control, and side effect minimization.

Analysis will occur upon completion of study enrollment. The co-investigators plan to prepare at least one manuscript for submission to a peer-reviewed journal. In addition, the co-investigators will present the results of the study at conferences and meetings where appropriate.

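### The control arm's 20 mL of 1% lidocaine is labelled 120 mg in both places where that arm is defined; the protocol's own conversion gives 200 mg, the full cited 90-minute maximum

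*Combined protocol and SAP*

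**What the plan says.** The control arm is defined twice, once in the rationale (1.1.1) and once in the arm definitions (1.2.5). Both times the syringe line reads "Syringe loaded with 20 mL of 1% lidocaine (120 mg); 22-gauge spinal needle". The matching line for the experimental arm reads "Syringe loaded with 12 mL of 1% lidocaine (120 mg); 22-gauge spinal needle". The two arms therefore carry the same milligram dose for different volumes of the same solution.

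The other statements that bear on the dose are these:

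- Section 1.1.1 cites the lidocaine label for paracervical block as setting a "maximum dose of 200 mg (20 mL at 1%) of lidocaine per 90-minute period".
- Section 1.2.4 repeats the 200 mg limit, adds 100 mg per side, and says that "the maximum dose should not be exceeded" because of the risk of seizure and cardiovascular collapse.
- The hypothesis in 1.1.2 describes the control as a "2-site, 20 mL 1% lidocaine injection PCB (2 mL for tenaculum placement, 18 mL for paracervical block").
- In 1.2.5, after 2 mL at the tenaculum site, "The remaining 18 mL are slowly injected into the cervicovaginal junction in two equal aliquots".
- Section 1.6 describes the comparator as "a technique of cervical block using 20 mL 2-site injection".
- Section 1.2.7 provides for discontinuing "Participants requiring additional cervical anesthesia" during the procedure. It names no drug and no dose limit.

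**The concern.** The amount of lidocaine is what this trial varies, and the lines that define the arms give one milligram figure for 12 mL and 20 mL of the same 1% solution. Both cannot be right.

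Two things are at stake. First, the written arm definition hides the contrast under study. The rationale for the smaller volume is that toxicity symptoms are more likely with 20 mL, yet on the milligram figures the arms look identical. Second, the true control dose sits at the cited ceiling. A reader who takes 120 mg at face value would think there is room below 200 mg. That matters if a control participant needs more anesthesia, which section 1.2.7 expects may happen. Discontinuing her from the study does not limit what is then injected.

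**Working it through.** **Inputs, all from the protocol**

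- Conversion and maximum: 200 mg corresponds to 20 mL at 1%, per 90 minutes (1.1.1).
- Per-side limit: 100 mg (1.2.4).
- Experimental volumes: 2 mL at the tenaculum site, then 10 mL in two equal parts (1.1.1, 1.2.5).
- Control volumes: 2 mL at the tenaculum site, then 18 mL in two equal parts (1.1.1, 1.2.5).
- Printed dose: 120 mg in each arm.

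**Concentration**

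200 mg / 20 mL = 10 mg/mL. The experimental line gives the same: 120 mg / 12 mL = 10 mg/mL.

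**Dose = volume × 10 mg/mL**

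| | Tenaculum site | Each side | Total volume | Total dose | Printed |
|---|---|---|---|---|---|
| Experimental | 2 mL = 20 mg | 5 mL = 50 mg | 12 mL | 20 + 50 + 50 = 120 mg | 120 mg |
| Control | 2 mL = 20 mg | 9 mL = 90 mg | 20 mL | 20 + 90 + 90 = 200 mg | 120 mg |

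The experimental figure reproduces. The control figure does not.

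**Can 120 mg be recovered for the control arm?**

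- Whole syringe: 20 × 10 = 200 mg.
- Paracervical portion only: 18 × 10 = 180 mg.
- A true 120 mg would need 120 / 10 = 12 mL at 1%, which is the experimental volume, or 120 / 20 = 6 mg/mL, a 0.6% solution that appears nowhere in the protocol.

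The likeliest explanation is that the figure was carried over from the experimental line.

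**Size of the error**

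- Understatement: 200 − 120 = 80 mg.
- Relative to the true dose: 80 / 200 = 40%. Relative to the printed figure: 80 / 120 = 67%.

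**Room under the cited 200 mg per 90 minutes**

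- Control, implied by the label: 200 − 120 = 80 mg.
- Control, actual: 200 − 200 = 0 mg.
- Control, on the assumption that only the 18 mL paracervical portion counts: 200 − 180 = 20 mg.
- Experimental: 200 − 120 = 80 mg.

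Bounding case: if a clinician used all of the apparent 80 mg in a control participant within 90 minutes, the total would be 200 + 80 = 280 mg, and 280 / 200 = 140% of the maximum. This shows how far the label could mislead; it is not an expected exposure.

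The planned control block stays within both limits: 200 mg in total against 200 mg, and 90 mg per side against 100 mg.

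**The case against.** The strongest reply is that this is a slip in a parenthesis with no effect on conduct. The arms are defined, compared and administered by volume. The same line gives volume and concentration, which fix the dose, and no step asks anyone to measure milligrams. Providers are not blinded and know they have just injected 20 mL. Sections 1.1.1 and 1.2.4 state the limit correctly. An overdose would require a control participant to need more anesthesia, the clinician to choose lidocaine, the injection to fall within 90 minutes, and the clinician to trust the printed figure over the volume just given. Most of this stands. It is why the safety consequence is modest and why the 280 mg figure is only a bound. It does not make the figure right: section 1.2.5 is where the treatments are defined, and its stated dose for one arm is wrong.

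A second reply is that the documents do not say outright whether the 20 mg at the tenaculum site counts toward a limit set for paracervical block. That is a fair caution. However, the hypothesis in 1.1.2 treats the full 20 mL, tenaculum injection included, as the block, so zero room is the protocol's own reading. On the other reading the room is 20 mg, still far short of 80 mg.

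A third reply is that the error is cured by changing two numbers, and that the added sentences are a matter of preference. It is true that the label correction stands alone. The sentences are recommended because the dose is at its ceiling and 1.2.7 sets no limit on what may be added.

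**Conclusion.** The concern holds, and the figure is wrong as written. By the protocol's own conversion the control arm receives 200 mg, not 120 mg, an understatement of 80 mg (40% of the true dose) in both places where the arm is defined. The experimental label is correct. The error lies in the milligram figure, since the volume is 20 mL throughout. The true dose equals the cited 90-minute maximum without exceeding it. The only assumption is that the tenaculum injection counts toward that maximum, and it affects the remaining room (0 mg or 20 mg) but not the error in the label.

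This should be fixed, though its consequences are limited. The hypothesis, sample size and analysis do not use the milligram figure, and nothing in the documents shows that the planned contrast between arms was lost.

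**What to change.** 1. In 1.1.1 and 1.2.5, change the control arm's dose from 120 mg to 200 mg. Leave the experimental label as it is.
2. In 1.2.5, add beside it that this is the full 90-minute maximum cited in 1.2.4, made up of 90 mg per side plus 20 mg at the tenaculum site.
3. In 1.2.7, add that a control participant who needs more cervical anesthesia has no lidocaine allowance left within 90 minutes of the block.

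The first item is the necessary correction; the other two make its consequence plain to the person giving the block. The cost is two changed numbers and two sentences, with no change to design, sample size or analysis.
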